5.1.1.1 Common Conventions

5.1.1.1.1 Analysis Periods

- Participants will receive treatment at the outset of the study (treatment group) or have treatment delayed until Month 3 (control group). The delayed treatment for control group is optional and referred to as “Optional Treatment”.
- Participants in the treatment group may receive optional touch-up treatment at Day 30 or optional repeat treatment at the completion of Month 12.
- Participants in the control group may receive optional touch-up treatment at Day 30 after optional treatment.
- Analysis periods are defined in [Table 5-1](#) below.

Table 5-1 Analysis period definition

Randomization Group	Period	Treatment Group Label	Start Date	End Date
Treatment	CP	VOLBELLA	Initial treatment date	The date of effective assessment for Month 3. 
 • If multiple assessments fall into Month 3 window, the date of the assessment included in the Month 3 analysis will be used as end date. • For participants who exit before Month 3, the end date is study exit date. • For participants with missing assessment at Month 3, the target day for Month 3 (Day 91) will be the end date.
	TP (12-Month)	VOLBELLA	Initial treatment date	Study exit date or date prior to repeat treatment, whichever is earlier
	Repeat Treatment Period	VOLBELLA	Repeat treatment date	Study exit date
Control	CP	Control	Randomization date	For participants who do not receive optional treatment: 
 • If multiple assessments fall into Month 3 window, the date of the assessment included in the Month 3 analysis will be used as end date. • For participants who exit before Month 3, the end date is study exit date. • For participants with missing assessment at Month 3, the target day for Month 3 (Day 91) will be the end date. For participants who receive optional treatment: 
 • The day before optional treatment
	TP (9-Month)	VOLBELLA Post-Control	Optional initial treatment date	Study exit date

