5.1.1.6.1 Adverse Events

An AE will be considered a TEAE if:

- The AE began on or after the date of the first dose of study intervention; or
- The AE was present before the date of the first dose of study intervention, but increased in severity or became serious on or after the date of the first dose of study intervention; or
- For the control group, AE began on or after the date of randomization; or
- For the control group and prior to the initial treatment, if AE was present before randomization, but increases in severity on or after randomization date, the AE is considered as TEAE.

An AE will be considered a treatment-emergent SAE if it is a TEAE that additionally meets any SAE criteria.

AEs and encompassing abnormalities, reported as occurring after the Screening Visit, will be coded using MedDRA version 20.1 or newer. A listing for all TEAEs in the treatment and control groups will be presented. AEs that occur before initial treatment for the treatment group and randomization for the control group will be listed. Additionally, unique participants reporting AEs as well as the number of events in the following AE categories will be summarized for treatment participants, control participants after optional treatment, and all treated participants as follows:

Table 5-7 AE Summaries

Endpoint	Description	Timing	Methodology
Overall summary	Overall summary only for the following categories: 
 • TEAEs • Treatment-related TEAEs • Treatment-related TEAEs at injection site • Treatment-related TEAEs not at injection site • SAEs • Treatment-related SAEs • Treatment-related SAEs at injection site • Treatment-related SAEs not at injection site • Discontinued due to TEAE • Deaths 	
 • CP • TP (12-Month) • Repeat Treatment Period • TP (9-Month) 	Categorical counts, Event descriptive
TEAEs	
 • Overall Summary and by SOC, PT 		Categorical counts, Event descriptive
TEAEs	
 • Overall summary and by SOC, PT and severity 		Categorical counts, Event descriptive
Treatment-related TEAEs	
 • Overall summary and by SOC, PT 		Categorical counts, Event descriptive
	
 • Overall summary and by SOC, PT and severity 		
	
 • Summary by duration, time to onset, severity, causality, treatment required, and outcome 		

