Note: SOCs and PTs will be sorted in descending frequency in the treatment group, then control group. AEs for control group before and after optional treatment are summarized separately.

For participants who receive repeat treatment, their AEs reported during the first months in the initial treatment period will be summarized and presented in parallel with AEs reported during the repeat treatment period.

Overall summary by severity for TEAEs and treatment-related TEAEs will also be summarized by the primary injection instrument used (needle vs cannula).

If more than 1 AE is coded to the same PT for the same participant, the participant will be counted only once for that PT using the most severe and most related occurrence for the summarizations by severity and by relationship to study intervention.

Time to onset for TEAEs will be computed as

$$\text{AE start date} - \text{reference date} + 1,$$

where the reference date is initial treatment date for TEAEs occurring on or after initial treatment but before touch-up treatment and the reference date is touch-up treatment date for TEAEs occurring on or after touch-up treatment but before repeat treatment.

Duration for TEAEs will be computed as AE end date – AE start date + 1. If AE end date is not available, duration for TEAEs will not be computed.

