6.3 Missing/Incomplete Date Conventions

Dates may be imputed with year, month, and day values under certain scenarios:

Table 6-4 Imputation Scenarios

Scenario	Complete			Imputable
	Year	Month	Day	
1	Yes	Yes	Yes	Complete
2	Yes	Yes	—	Yes
3	Yes	—	Yes	No ^a
4	Yes	—	—	Yes
5	—	Yes	Yes	No ^a
6	—	Yes	—	No ^a
7	—	—	Yes	No ^a
8	—	—	—	Yes

^a Not allowed per database design.

Dates will be imputed initially toward a specified target date for imputable scenarios 2, 4, and 8, and adjusted against the latest reasonable dates. The initial imputed date is determined by the following algorithm:

Table 6-5 Initial Imputed Date Algorithm

Available Year (YYYY)	Available Month (MM)			
	Missing	< Target Month	= Target Month	> Target Month
Missing	Target Date	—		
< Target Year	YYYY-12-31	YYYY-MM-LD		
= Target Year	Target Date	YYYY-MM-LD	Target Date	YYYY-MM-01
> Target Year	YYYY-01-01	YYYY-MM-01		

LD = last day of the month; MM = available start date month; YYYY = available start date year.

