6.3.1 Missing/Incomplete AE Start Date

Imputation of dates with missing day and/or month is only applied to TEAEs. If adequate information is available, no imputation is needed. TEAE start dates with missing day or month will be imputed as following:

- If day and month are missing but year is available, then the imputed day and month will be 01 Jan or the initial treatment date if they have the same year, whichever is later (because TEAE onset is not expected prior to administration of study treatment)
- If day is missing but the month and year are available, then the imputed day will be the first day of the month or the initial injection date if they have the same month and year, whichever is later.

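### The rule for partial AE start dates has no repeat-treatment or touch-up floor, so a missing-day AE that follows re-injection can be dated before it and given an onset time of about a year

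*SAP*

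**What the plan says.** SAP 6.3.1 gives two rules for a partial TEAE start date. With the day missing, "the imputed day will be the first day of the month or the initial injection date if they have the same month and year" (the later of the two). With day and month missing, it is "01 Jan or the initial treatment date if they have the same year, whichever is later". The reason given is "because TEAE onset is not expected prior to administration of study treatment". Neither rule mentions touch-up or repeat treatment.

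The general text in SAP 6.3 says "Dates will be imputed initially toward a specified target date for imputable scenarios 2, 4, and 8" and then adjusts against the latest reasonable dates. It names no target date for AEs.

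These dates feed three outputs:

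- **Periods.** SAP Table 5-1 ends TP (12-Month) at "Study exit date or date prior to repeat treatment, whichever is earlier". The Repeat Treatment Period starts on the repeat treatment date.
- **Time to onset.** SAP 5.1.1.6.1 computes AE start date minus reference date plus 1. The reference is initial treatment for TEAEs before touch-up. After that, "the reference date is touch-up treatment date for TEAEs occurring on or after touch-up treatment but before repeat treatment". No reference is given for TEAEs on or after repeat treatment. Table 5-7 lists a "Summary by duration, time to onset, severity, causality, treatment required, and outcome" for treatment-related TEAEs.
- **Initial against repeat.** For participants who have repeat treatment, AEs from the first months after initial treatment are "presented in parallel with AEs reported during the repeat treatment period".

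Table 6-1 counts Safety Day after repeat treatment from the repeat treatment date.

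**The concern.** The floor keeps a TEAE from being dated before the treatment it followed, but it is tied to the first treatment only. In the month of repeat treatment it cannot operate, because the initial injection was about a year earlier. An acute reaction to re-injection with a missing day can therefore be dated before the re-injection. In the time-to-onset summary it would look like a late reaction to the first course, and Protocol 11.1.1 names delayed effects many months after treatment as a known risk.

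Elsewhere the SAP resolves missing AE information cautiously: in Table 6-6, missing intensity in the treatment period becomes severe and missing relationship becomes related. The date rule at re-injection does not follow that pattern. What is at stake is the accuracy of a few entries in descriptive safety tables.

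**Working it through.** There is no stated figure to reproduce. The check applies the written rule to calendar dates.

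**Inputs.** The start-date rule is from SAP 6.3.1 and the onset formula from SAP 5.1.1.6.1. Month 12 is counted from the last treatment, initial or touch-up (Protocol 6.2.3.1). Repeat treatment is 0 to 14 days after the Month 12 visit, with 1 month of follow-up (Protocol 6.2.3.2). Assumption: Month 12 is day 365 after the last treatment.

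**1. One case at repeat treatment.** Touch-up is on 10 Feb 2018 and repeat treatment on 20 Feb 2019. An AE begins on 21 Feb 2019 and is recorded as Feb 2019.

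- Imputed start: 01 Feb 2019. TP (12-Month) ends on 19 Feb 2019, so this date falls inside it.
- Onset from touch-up: 01 Feb 2019 − 10 Feb 2018 + 1 = 357 days.
- Safety Day from repeat treatment: 01 Feb − 20 Feb + 1 = −18.
- True value: 21 Feb − 20 Feb + 1 = day 2.
- With only the year known, the start becomes 01 Jan 2019: 01 Jan 2019 − 10 Feb 2018 + 1 = 326 days.

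**2. Range.** Let repeat treatment fall on day *d* of its month (*d* = 2 to 31) and *L* days after Month 12 (*L* = 0 to 14).

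- Onset = 365 + *L* − (*d* − 1) + 1. Minimum 365 + 0 − 30 + 1 = 336; maximum 365 + 14 − 1 + 1 = 379.
- Safety Day = 1 − *d* + 1 = 2 − *d*, which runs from 0 to −29.
- With an assumed ±14-day window for Month 12, the onset range widens to 322 to 393.

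**3. How often the calendar produces it.** Take each of the 365 dates of 2019 as the repeat date, with onset *k* days later and the day missing. The AE is set before repeat treatment when onset is in the same month and repeat treatment was not on the 1st. The count is 365 − 12(*k* + 1).

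| Onset after repeat treatment | Set before repeat treatment |
|---|---|
| same day | 353/365 = 96.7% |
| 1 day | 341/365 = 93.4% |
| 3 days | 317/365 = 86.8% |
| 7 days | 269/365 = 73.7% |
| 14 days | 185/365 = 50.7% |

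At initial treatment the floor operates and the count is 0/365. These are shares of missing-day AEs under evenly spread dates. They do not say how many such AEs there will be.

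**4. One case at touch-up.** Initial treatment is on 11 Jan 2018 and touch-up on 10 Feb 2018. An AE begins on 11 Feb and is recorded as Feb 2018. The rule gives 01 Feb, so onset = 01 Feb − 11 Jan + 1 = 22 days from initial treatment. The true value is 11 Feb − 10 Feb + 1 = 2 days from touch-up. TP (12-Month) spans both dates, so that period does not change.

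**5. Which outputs change at repeat treatment.** The SAP does not say how an AE enters a period.

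- By start date: the AE leaves the Repeat Treatment Period and carries 357 days.
- By when it was reported: it stays in the Repeat Treatment Period but carries 357 days, or −18 on the Table 6-1 scale.

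For scale under the first reading only: 140 × 3/4 = 105 treated, and × 0.80 for the protocol's 20% dropout = 84. With an assumed repeat uptake of 50% to 80%, that is 42 to 67 participants. One displaced AE takes a preferred-term row from 1/42 = 2.4%, or 1/67 = 1.5%, to 0%.

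**The case against.** - **The period effect rests on an unstated convention.** The parallel display speaks of AEs reported during the repeat period, and table specifications sit in a separate document. This stands. A reader might infer that the rule makes repeat treatment look safer. The documents do not support that as a general statement, because it holds only if AEs are assigned by start date, which the SAP never says.
- **The rule is the same at both treatments.** It takes the earliest date compatible with the known parts and with TEAE status. After a year of exposure, onset earlier in the repeat month is possible. This also stands: the rule is right for an AE that did begin earlier that month. It is wrong for any AE that began after a repeat treatment given later than the 1st of that month.
- **Missing days are least likely where the shares are highest.** Sites record AEs on the treatment day, telephone on day 3 and see the participant on day 14. AEs are solicited at every contact. So the 97% and 87% should not be read as rates expected in this trial.
- **Acute reactions are largely captured elsewhere.** Diary ISRs are summarised by treatment (Table 5-8) without using 6.3.1. SAEs and vision-related AEs are reported within 24 hours of awareness. This stands and limits the harm.
- **SAP 6.3 might supply the floor.** It would if a programmer took repeat treatment as the target date, but the SAP does not say so and 6.3.1 is the AE-specific rule. The statement that no imputation is needed when information is adequate does not cover a day that is actually unknown.

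**Conclusion.** The rule is wrong as written for a narrow set of AEs: those that began after repeat treatment in the same month, with the day missing and repeat treatment not on the 1st. Their imputed start precedes the treatment they followed. Their onset reads about 336 to 379 days, or Safety Day 0 to −29, instead of days. The range assumes Month 12 on day 365 and repeat treatment 0 to 14 days later. The gap at touch-up is of the same kind.

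A move from the Repeat Treatment Period to TP (12-Month) follows only under assignment by start date. Bias in favour of repeat treatment is therefore a possibility, not a finding.

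The effect is confined to descriptive AE tables. TEAE status, diary ISRs, listings of the actual partial dates and all hypothesis tests are unaffected. The number of partial dates is not in the documents and is probably small. Priority: minor.

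**What to change.** In SAP 6.3.1, add:

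> If the known month and year (or known year) contains a touch-up or repeat treatment date, and the AE was first recorded at a contact after that treatment, having not been recorded at or before the pre-treatment AE query, and its end date is not before that treatment, impute the start date as that treatment date; otherwise the existing rule applies.

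In SAP 5.1.1.6.1, state that AEs are assigned to periods by start date, imputed where partial. Add the repeat treatment date as the time-to-onset reference for TEAEs that start on or after it, in line with Table 6-1.

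In the repeat-treatment case above, the start becomes 20 Feb 2019, in the Repeat Treatment Period, with onset 20 Feb − 20 Feb + 1 = day 1 against a true day 2.

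The condition on first recording is needed. With the end date as the only safeguard, an ongoing AE noted at the Month 12 visit shortly before repeat treatment would be dated after it was recorded. A year-only AE from January could be moved forward by months.

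The cost is one clause and two sentences, using dates that sites already record. The downside is that an AE that truly began earlier, but was first mentioned only after the treatment, would be attributed to that treatment. That is a small error on the conservative side.

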6.3.2 Missing/Incomplete AE/Medication End Date

Imputation of dates with missing day and/or month is only applied to TEAEs when AE duration is calculated. If adequate information is available, no imputation is needed. TEAE end dates with missing day or month will be imputed as following:

- If day and month are missing but year is available, then the imputed day and month will be 31 Dec or the study exit date if they have the same year, whichever is earlier

If day is missing but the month and year are available, then the imputed day will be the last day of the month or the study exit date if they have the same month and year, whichever is earlier.

6.4 Safety Endpoint Conventions

6.4.1 Adverse Events

6.4.1.1 Missing Intensity or Relationship

If the investigator is unable to provide the actual values, the following imputations will be applied:

Table 6-6 Missing AE Intensity and Relationship Imputation Algorithms

Missing Value	Imputation	Timing
Intensity	Mild	Screening Period, Pretreatment Period,
	Severe	Treatment Period
Relationship	—	Screening Period, Pretreatment Period
	Related	Treatment Period

6.4.1.2 Character Values

Character values (eg, < 5, negative) will be reviewed prior to database lock and converted to numeric values for analysis as appropriate. These conversions will be documented in the ADaM specifications.

[figure not shown]
6.5 Imputed Value Listing Conventions

In general, listings will present the actual partial or missing values rather than the imputed values that may be used in endpoint derivation. In instances where imputed values will be presented, imputed values will be flagged. Actual rules will be fully defined in the table, figure, and data listing specification document.

7. SAP Version History

SAP Version History Summary		
SAP Version	Approval Date	Change
1	May 1, 2018	Not Applicable
2	Mar 11, 2019	
 • Clarify safety population definition • Change ISR days to ISR duration • Clarify prior and concomitant medication definition • Editorial changes
3		
 • Defined analysis periods • Add VIT population • Add VRT population • Add VOT population • Changed primary endpoint analysis from as-observed to multiple imputation • Editorial changes
		
 • Removed change from baseline analysis for assessment of dark circles and individual FACE-Q items
		
 • Included the FACE-Q – Appraisal of Lower Eyelids questionnaire in the Appendix

ALLERGAN

1932-701-008 Statistical Analysis Plan
